Identification and treatment of gait abnormalities in children and adolescents with Dravet syndrome

Research Protocol for posting on ClinicalTrials.gov PRS

Protocol Registration number: NCT03857451

Date: 07 February 2017

1. Background

The gait pattern in children and adolescents with DS was first described as "crouch gait" by Rodda et al., using 2D video analysis, clinical examination and X-ray of the lower limbs [1]. Later, Rilstone et al confirmed this "crouch" pattern in adults [2]. In addition to the gait deviations described, the children with DS also showed an enlarged internal hip rotation and a decreased passive knee and hip extension and an increased external tibial torsion and pes plano valgus observed with increasing age [1]. Based on these observations, Rodda hypothesised that a combination of malalignment and muscle weakness of the lower limbs lies at the root of the observed gait disorders [1]. However, this hypothesis can only be confirmed by 3D gait analysis in combination with measurements of muscle strength, which has not yet been carried out.

From the study of Rodda et al. "crouch gait" appears to develop in children with DS between 6 and 12 years [1], followed by a progressive decline in the gait pattern with increasing age [1, 2]. As mentioned, the passive movement limitations and the bony deformities aggravate by increasing age [1]. It is known that "crouch gait" in other patient populations usually arises in early adolescence [3]. This period is characterized by a growth spurt, in which body length and weight increase faster than muscle strength, reflecting the "crouch" pattern [3]. "Crouch gait" is known as a very complex, progressive disorder, profound understanding of the various causal factors is required to adequately treat this pattern. In order to gain full insight into the causes of the abnormal gait pattern, a longitudinal follow-up of patients is therefore necessary to monitor the influence of various factors, such as growth, a possible decrease in muscle force, but also the characteristic psychomotor retardation.

No literature is known on the treatment of gait disorders in patients with DS. Researchers do mention the use of corrective insoles [4], orthopaedic shoes and ankle-foot orthosis [1], mainly based on clinical expertise and results of scientific research in other populations. Orthopaedic procedures are also applied to correct bone-like abnormalities with the aim of optimizing the gait pattern [1]. The effectiveness of these interventions in patients with DS is unknown. To increase the quality of life of the individual patient, it is essential to keep patients with DS active and mobile for as long as possible. Interventions can focus on improving the strength and/or correction of the biomechanics of the gait pattern. It is extremely important to also think about prevention and determine at what age one can already intervene to correct small deviations in biomechanics (e.g. by splints) to prevent children from entering a vicious circle of serious gait disorders, such as "crouch". When drawing up a treatment plan, it is possible to rely on the expertise of the treatment of gait abnormalities in other neuromotor disorders (cerebral palsy, spina bifida), but it is essential to adapt the proposed treatment plan to the specific characteristics of patients with Dravet syndrome.

2. Purpose of the research

The ultimate objective of this project is to draw up adequate, scientifically based, treatment for reduction and, if possible, prevention of gait disorders in children with DS.

3. Method

The research consists of 2 parts: a retrospective part and a prospective part. In the retrospective part, children's developmental status and potential developmental delay is described based on file data. In the prospective part, the children with DS are contacted and their gait pattern is evaluated.

Patient Recruitment:

Dravet syndrome has a prevalence of 1/15,000 to 1/30,000. In Flanders, an estimated 380 people would have been diagnosed with Dravet syndrome. In 2016, 70 patients were medically and paramedically monitored at the University Hospital Antwerp (UZA), at the Child Neurology Department. As this is a rather small patient population, attempts are made to reach all patients within the age range of 3 – 25 years with Dravet syndrome in the geographical area of Flanders and the south of the Netherlands. Approximately 50 participants are being sought, 30 of which are from UZA and 20 from other centres. Children can participate in the study if they are (1) diagnosed with Dravet syndrome, based on the criteria defined by Ceulemans and Cras in 2004 [5] and (2) are 3 years or older, have at least one year of walking experience and are up to 25 years at first inclusion. Exclusion criteria for participation are the prevention of a heavy epileptic seizure (status epilepticus or tonic-clonic seizure for more than 3 minutes) in the 24 hours prior to the study and/or insufficient cooperative for the removal of a 3D gang analysis.

A study officer from the UZA will invite patients who arrive at the Dravet consultation at the Child Neurology Service to participate in the study. In addition, a written call is launched via the newsletter of the parent association Stichting Dravet Syndrome Nederland/Vlaanderen. Interested parties can contact the aforementioned research officer who will provide further information.

Written consent is requested to the parent(s) or legal guardian of the children. The parents and the child are informed prior about the course of the study, expectations and risks.

A control population in accordance with the size and characteristics of the pilot group, of children and (young) adults with typical development or cerebral palsy will be composed of available data from previous research. UZ Leuven makes a database available to this end of gait analyses carried out for research at the KU Leuven [6]. In addition, a second control group will be composed of children and young adults who also have motor and developmental problems, whether or not in combination with epilepsy, due to a genetic condition that is not a mutation in the SCN1A gene.

Research Setting

All studies carried out for this study will take place in the M²OCEAN lab, UZA.

Data Collection Procedures

The research protocol is Figure 1 and a schematic view can be found in the addendum to this research protocol. Prior to the physical examination, parents are asked about the use of technical aids as well as the distance that the child can walk independently, and a classification is made according to the Functional Mobility Scale [7]. The Mobility Questionnaire, research version (MoVra28) is also taken [8].

An essential part of a gait analysis is an extensive physical neurological and clinical physiotherapeutic examination [9]collecting information on joint range of motion, alignment (femoral anteversion, bimalleolar and tibiofemoral angle via goniometry), muscle strength of the lower limbs, as well as about possible foot abnormalities (varus or valgus abnormalities of rear foot) and and hypermobility (Beighton hypermobility scale). Children with DS usually have a severe mental retardation which makes instructions for manual muscle strength tests difficult to understand. The physiotherapeutic exam will therefore be supplemented by the Functional Strength Measurement [10], a strength test designed especially for children with easy to understand assignments. The results of the FSM in children with Dravet syndrome can be compared with available normative values from the literature [10].

[figure not shown]

Figure 1: Schematic overview of the research protocol

In order to characterize the biomechanics of the gang pattern, the children will be subjected to an extensive 3D gait analysis. The experimental set-up used has already been validated in several studies [11-13] and consists of an instructed walkway (16 m long), surrounded by 8 cameras (Vicon Motion Systems, T10, 100Hz), in which four force platforms (AMTI type OR 6-7, 0.5 x 0.4 m, 1000 Hz), were built in to register the ground reaction forces of the left and right foot separately. The Helen-Hayes marker set-up [14] (see fig. 2) will be used to follow the kinematics of the lower limbs. The reflective markers (14 mm) are applied to the skin using hypoallergenic tape. The children will be encouraged to walk barefoot on the hiking trail at preferential speed. The over and over again steps are repeated until 3 good left and 3 good right-wing foot contacts are collected on the power plates. In order to achieve a pattern as naturally as possible, the children will receive small assignments (e.g. bringing small cubes or puzzle pieces back and forth) to divert attention from stepping.

[figure not shown]

Figure 2: The marker set

Data analysis

Kinematic data, such as the range of motion of the different joints, describe the gait pattern and a comparison with age-specific reference data may determine gait abnormalities. The Vicon Clinical Model (based on the Kadaba [15] and Davis [14]) is used to reconstruct movements of the different body segments and describe and analyze the kinematic time profiles. Joint angles are expressed as YXZ Cardan angles of the most distal compared to the most proximal segment. The angles are zero during the upright stance. These angles display flexion/extension, ad/abduction and internal/external rotation of the joints.

To detect the biomechanical causes of the gait disorder, it is important, using an integrated inverse-dynamic model (Vicon Clinical Model), to determine the forces that control the observed movement. From measured joint kinematics and the ground reaction forces, net joint moments are calculated, which may be considered the cause of the observed movement pattern in a specific joint. The net joint moment is the resulting moment generated by all the structures that span the joint (muscles, ligaments, capsule, skin) [16]. To fully understand how active (muscles) and passive (gravity, ligaments and capsule) forces work together during movement, the inverse dynamic analysis must be supplemented by electromyography (EMG). To the extent of the possible, we will therefore attempt to collect EMG data from the hip extensors, knee flexors and extensors and ankle plantar flexors.

Interventions

No literature has been known to date on the treatment of arising disorders in patients with DS. There are three possible approaches to the prevention and treatment of gait disorders (1) the changes in passive anatomy; (2) changes in active anatomy and (3) the changes in the gait

pattern due to change in internal forces (active and passive anatomical changes) and external forces (ground reaction force, gravity).

Passive changes mean muscle contractures and bone-like abnormalities. Previous research identified both flexion and extension defects, as well as malrotations in children with DS [1]. Prevention of muscle contractures can be done by stretching during physiotherapy as well as by using night equipment for positioning. Active changes mean that we have a loss of strength that was suggested in children with DS [1]. Here too, after sufficient insights into the natural course, preventive, but also corrective action can be done using physiotherapy. Finally, there are also possibilities to directly affect the gait pattern, for example, by using orthotics that can restore biomechanical functions.

Use of orthotics as well as frequency of physiotherapeutic interventions will be listed. On the basis of the results of the 3D gait analysis and the longitudinal follow-up of patients, a decision will be taken on the usefulness and application of any interventions in consultation with the treating neurologist and physiotherapist.

Statistical analysis plan

The statistical analysis will mainly include descriptive statistics. Gait parameters will be compared between DS and healthy controls using a t-test or a non-parametric alternative. Changes in gait pattern, detected by annual retesting, will be evaluated using a mixed models design.

4. Relevance of the research

Knowledge and insights from this project will directly improve quality of life in patients with Dravet syndrome by optimizing the treatment of gait abnormalities, allowing the individual to remain mobile for longer and thus contribute to increased independence and self-reliance of the individual. This sets the research within the strategic cluster 'Health & Well-being' with a focus on prevention and treatment of gait problems in brain disorders based on personalized therapy. A personalised treatment plan can only be achieved if a thorough identification of the gait defects and its causes have been carried out, which can only be done on the basis of 3D gait analysis. Moreover, prevention can only be done and intervened early, when the data of a longitudinal follow-up of the gait pattern are available in children with DS.

5. References

- 1.Rodda, J.M., et al., *Progressive gait deterioration in adolescents with Dravet syndrome*. Arch Neurol, 2012. **69**(7): p. 873-8.

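### Does excluding children who cannot cooperate with the 3D gait analysis wrongly remove them from a prospective description of mobility?

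*Protocol*

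**What the plan says.** Patient Recruitment (section 3) introduces the criteria with "Exclusion criteria for participation are the prevention of a heavy epileptic seizure" and adds, joined by and/or, that a child who is "insufficient cooperative for the removal of a 3D gang analysis" is excluded. Either condition is enough alone. The same section gives the target: "Approximately 50 participants are being sought, 30 of which are from UZA and 20 from other centres".

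The opening of section 3 defines the prospective part: "In the prospective part, the children with DS are contacted and their gait pattern is evaluated". Data Collection Procedures starts with items that need no walkway: "Prior to the physical examination, parents are asked about the use of technical aids", together with independent walking distance, a Functional Mobility Scale class and a mobility questionnaire. The walkway, cameras and force plates belong only to the 3D analysis described later in that section.

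The Statistical analysis plan paragraph announces mainly descriptive statistics, a comparison of gait parameters between Dravet patients and healthy controls, and a mixed model for yearly change in gait pattern.

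**The concern.** The criterion is written as a bar to participation, not as a condition for one measurement. Taken at face value, an otherwise eligible child who cannot manage the walkway contributes nothing prospectively, although the mobility items could still be collected. If untestable children are the more severely affected, which is plausible but not stated, the mobility data would describe a milder group.

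Two sentences in the Background seem to make that loss relevant: "it is essential to keep patients with DS active and mobile for as long as possible", and the account of crouch gait as "followed by a progressive decline in the gait pattern with increasing age". What would be at stake is a mobility description that looks better than the truth in a small, rare population.

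**Working it through.** The protocol states no figure to reproduce: it gives neither an untestable share nor a precision target. The check is therefore mainly of the text, with an illustration of size.

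**1. What is the prospective part for?** Section 3 says evaluation of the gait pattern. The Background says the hypothesis on causes can be confirmed only by 3D gait analysis combined with strength measurement. Section 4 says the gait defects and their causes can be identified only by 3D gait analysis. The named comparisons concern gait parameters and gait pattern. No section sets an aim of estimating mobility in all Dravet patients. The early items in Data Collection Procedures can reasonably be read as characterising the children whose gait is measured, and for that use restricting them to those children is right.

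**2. Do the two Background sentences create such an aim?** No. The first concerns quality of life. The second describes decline of the gait pattern, not of mobility class.

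**3. At what level does the criterion act?** The literal reading is participation. Four features weaken it:
- The companion criterion looks back only 24 hours for a heavy seizure. That is a passing state, sensible for a test day and hardly a reason to bar a patient from a project with yearly retests.
- Research Setting uses the word study for a single examination: "All studies carried out for this study will take place" in one laboratory.
- The upper age limit is set at first inclusion, which may imply that inclusion recurs at later sessions.
- The sentence is a faulty translation: taken literally it excludes the prevention of seizures and speaks of removing an analysis. Its exact level carries little weight.

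In addition, the questions to parents precede the physical examination, and nothing says answers already given are discarded.

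**4. How large could the effect be on the literal reading?** Let p be the share of otherwise eligible children coming forward who cannot complete the 3D test, x the proportion in some mobility category among tested children, and y that among untestable children. The proportion in all is (1−p)x + py, so it differs from x by p(y−x), in absolute value at most p.

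| Assumed p | Largest shift in a mobility proportion | Enrolled to give 50 with 3D data, 50/(1−p) | 3D data if 50 is the total, 50(1−p) | Standard-error ratio, 1/√(1−p) |
|---|---|---|---|---|
| 5% | 5 points | 52.6 | 47.5 | 1.026 |
| 10% | 10 points | 55.6 | 45 | 1.054 |
| 20% | 20 points | 62.5 | 40 | 1.118 |

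The shift column has zero as its lower end (y = x), and its upper bound holds for any exclusion of a share p. The last three columns do not describe harm from the present text. They show the price of keeping untestable children: about 3, 6 or 13 more families if the target counts children with 3D data, or standard errors of 3D means larger by 2.6%, 5.4% or 11.8% if the total stays at 50.

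**5. Does any named comparison change?** No. A child without a completed walkway test supplies no 3D data under either wording, so the comparison with controls and the model for yearly change gain nothing. The retrospective part rests on file data and is probably untouched.

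**The case for a change.** The strongest case is that the text does say participation, that either criterion suffices alone, and that no visible section keeps an untestable child for the other items. Recruitment tries to reach every patient aged 3 to 25 in the region because the population is small. Severe intellectual disability is described as usual and as an obstacle to following strength-test instructions, so failure to cooperate is unlikely to be random. For EMG the protocol already sets feasibility at the level of the measurement (Data analysis). Use of orthotics and frequency of physiotherapy, listed under Interventions, need no walkway either. Nor can a statistical analysis plan recover data from children who were never enrolled.

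Much of this stands as a description. The literal reading is a fair reading, and the mobility items, if reported, describe children who could be tested and should be labelled so. What does not follow is a fault. Dropping the criterion would still not give a representative picture of mobility, because entry also requires one year of walking experience and runs through one clinic's consultation and a newsletter. Keeping untestable children under yearly follow-up would bring their families to a single laboratory for visits that yield no 3D data. Whether that is worthwhile is a choice of design. Figure 1 and the addendum are not visible, so silence in the remaining text on such children is weak evidence.

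**Conclusion.** The concern does not hold. Cooperation with the 3D gait analysis is a coherent entry condition for a prospective part defined as evaluation of gait. The harm depends on a literal reading of a mistranslated sentence, and on an aim of describing mobility that the protocol does not state. The possible shift in a mobility proportion lies between zero and the untestable share; the values of 5%, 10% and 20% are assumptions, since the protocol supplies none. The effect on the named gait comparisons is nil. Whether the criterion applies per test day is a fair question of wording, but neither answer alters those comparisons. The conclusion would differ if the protocol set out to estimate mobility in all Dravet patients, and it does not.

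### Matching the archive control group to the size of the Dravet group may give up precision that existing records could supply at little cost

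*Protocol*

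**What the plan says.** All of the sizing text is in the Protocol, section 3 (Method), under Patient Recruitment.

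- **Dravet group:** "Approximately 50 participants are being sought, 30 of which are from UZA and 20 from other centres". The reason given for the limited number is rarity: "As this is a rather small patient population, attempts are made to reach all patients within the age range of 3 – 25 years".
- **Archive controls:** "A control population in accordance with the size and characteristics of the pilot group", continuing "of children and (young) adults with typical development or cerebral palsy will be composed of available data from previous research". I take the pilot group to be the Dravet participants.
- **Source:** "UZ Leuven makes a database available to this end of gait analyses carried out for research at the KU Leuven". The number of records is not given, nor is the split between typical development and cerebral palsy.
- **Other controls:** a further group with other genetic conditions is called the second control group. Typical development and cerebral palsy therefore stand together as the first.

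Under Statistical analysis plan, the only between-group test named is this: "Gait parameters will be compared between DS and healthy controls using a t-test or a non-parametric alternative". No significance level, power, effect size or SD is stated, and the analysis is described as mainly descriptive.

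**The concern.** Matching on characteristics such as age protects a comparison from confounding. Matching on size does not. A 1:1 ratio is efficient when each control costs about as much as each patient to recruit and measure. Here the controls have already been measured, and the Dravet number cannot easily grow because the plan already tries to reach every patient in the region. The number of controls is then one of the few inexpensive ways left to sharpen the Dravet-versus-healthy comparison, and the recruitment text ties it to the Dravet number without saying why.

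The same sentence places typically developing and cerebral palsy records in one population. If a single total of about 50 covers both, the healthy group in the test would be smaller than 50. At stake is the width of the confidence intervals for each gait parameter, not the validity of the comparison.

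**Working it through.** The Protocol gives no precision or power figure, so there is nothing of its own to reproduce.

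**Inputs from the Protocol**
- Dravet participants: 30 + 20 = 50.
- Archive controls under the size rule: about 50.

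**Assumptions, because the Protocol gives no figure**
- Eligible typically developing records: 100 to 200.
- Common within-group SD of 1, so results are in SD units.
- Two-sided 5% level; 80% power for the detectable difference; a true difference of 0.5 SD for the power column.

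**Formulas**
- SE of the difference = √(1/50 + 1/n), where n is the number of healthy controls.
- Detectable difference = (1.960 + 0.842) × SE.
- Power at 0.5 SD = Φ(0.5/SE − 1.960).

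| Healthy controls | SE (SD units) | SE relative to 50 controls | Detectable difference (SD) | Power at 0.5 SD |
|---|---|---|---|---|
| 50 (as written) | √0.0400 = 0.200 | – | 0.560 | 70.5% |
| 100 | √0.0300 = 0.173 | −13% | 0.485 | 82.3% |
| 150 | √0.0267 = 0.163 | −18% | 0.457 | 86.5% |
| 200 | √0.0250 = 0.158 | −21% | 0.443 | 88.5% |
| no limit | √0.0200 = 0.141 | −29% | 0.396 | 94.2% |

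Seen from the other side, the SE with 50 controls is 0.200/0.173 = 1.15 times the SE with 100, and 0.200/0.158 = 1.26 times the SE with 200. That is the 15% to 26% excess. A noncentral t calculation changes power by a point or less (69.7% with 50 controls, 81.8% with 100, 88.3% with 200).

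**The ceiling.** The Dravet term, 1/50, does not change however many controls are added. The SE therefore cannot fall below √0.02 = 0.141, a cut of 1 − 0.141/0.200 = 29%. Most of the gain has been made by three or four controls per patient.

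**Effect of weighting.** The table treats every record as fully informative. If the archive has a different age mix and is weighted to the Dravet ages, its effective size is smaller than its count. For illustration, 150 records with an effective size of 100 would give an SE of 0.173, not 0.163.

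**The shared-population reading.** If the 50 archive records were split 25 and 25 between typical development and cerebral palsy (an assumed split), the SE would be √(1/50 + 1/25) = 0.245, the detectable difference 0.686 SD and the power at 0.5 SD 53.2%. This is one possible reading of an unclear sentence and is separate from the 1:1 question.

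**The case against.** The strongest objection is that the loss depends on a number the Protocol does not give. If the Leuven database holds about 50 or fewer eligible typically developing records across ages 3 to 25, the size rule excludes nobody and costs nothing. This stands, and it makes the point conditional.

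Second, the wording need not be a hard cap. It can be read as asking for a comparable group, and the English is loose elsewhere. This stands in part: the sentence sets no maximum, but it does name size as something to match.

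Third, the gain is modest, weighting would shrink it, and no power target is missed because none is set. All true. If healthy controls vary less than patients, the control term is a smaller share of the variance and the gain is smaller again. Extra records also take some work to select and process, so the saving is in recruitment and measurement only.

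A reader might infer more than the text supports in three places:

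- **Age-specific reference limits.** Under Data analysis the Protocol says "a comparison with age-specific reference data may determine gait abnormalities". One might conclude that limits of normal gait would rest on two or three controls per year of age. The Protocol does not say that these reference data come from this archive, and it defines no age bands or limits. Matching on characteristics would also place controls at the patients' ages, not evenly across the range. No figure for such limits is therefore offered.
- **Dilution by cerebral palsy records.** The text does not establish that one total of 50 covers both groups. The test itself is confined to healthy controls, so it does not pool them.
- **The t-test.** Unequal group sizes might seem to require a change of test. The term used already allows the Welch form, and that choice can be left to a statistical analysis plan.

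**Conclusion.** The point holds as a cheap improvement. The Protocol names size as a matching criterion for records that already exist, and the one reason it gives for small numbers applies only to the Dravet group.

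If 100 to 200 typically developing records are eligible, the rule makes the SE of the Dravet-versus-healthy difference up to about 15% to 26% larger than it need be. At a true difference of 0.5 SD, that is about 12 to 18 points of power (70.5% against 82.3% to 88.5%). These figures assume 50 Dravet participants, equal SDs, a two-sided 5% level and fully informative controls. After age weighting the gain is smaller.

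A reader might infer that precision is certainly being lost. The Protocol does not support that, because the archive size is unknown. Nor does the rule introduce bias or raise the type I error rate.

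**What to change.** In the Patient Recruitment sentence on archive controls:

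1. Remove size as a matching criterion and keep matching, or plan adjustment, on age and other relevant characteristics.
2. Use all typically developing records that meet the age and quality criteria, or match several per patient.
3. Count typically developing and cerebral palsy records as separate groups and state the number of each, so that the healthy comparison has its own size.
4. State how many eligible records the database holds. If it is about 50 or fewer, items 1 and 2 change nothing in practice; item 3 is still worth making.

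If the age-specific reference data under Data analysis are to come from this archive, say so there.

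The cost is a small edit to the text, a larger data extract and some processing. A larger archive set brings its own age mix, so matching or adjustment becomes necessary and takes back part of the gain. Nobody further has to be recruited or measured.

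### Joint moments recorded at self-selected speed go into an unadjusted comparison with healthy controls, so a difference in pace could be mistaken for a biomechanical cause of the gait disorder

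*Protocol*

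**What the plan says.** Four parts of section 3 (Method) of the protocol bear on this point.

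- **Data Collection Procedures.** Speed is left to the child: "The children will be encouraged to walk barefoot on the hiking trail at preferential speed". This is the only mention of walking speed in the protocol.
- **Data analysis.** Joint moments are derived from the measured kinematics and the ground reaction forces in order to detect biomechanical causes: "net joint moments are calculated, which may be considered the cause of the observed movement pattern in a specific joint".
- **Statistical analysis plan.** The group comparison is "Gait parameters will be compared between DS and healthy controls using a t-test or a non-parametric alternative". No covariate is named.
- **Patient Recruitment.** The controls come from data of previous research: "A control population in accordance with the size and characteristics of the pilot group". The characteristics are not listed, and speed is not named among them.

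The protocol also sets limits on what moments can show. Section 1 (Background) says of the malalignment-and-weakness hypothesis that "this hypothesis can only be confirmed by 3D gait analysis in combination with measurements of muscle strength". Data Collection Procedures includes a clinical strength examination and the Functional Strength Measurement. Data analysis says that a net moment sums the contributions of muscle, ligament, capsule and skin, and that EMG has to supplement it, although EMG is collected only as far as possible.

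**The concern.** Moments are computed from motion and ground reaction forces, and both can be expected to change with walking speed. If one group walks slower, its moments can differ without any other difference between the groups. A two-group test of moments then answers whether moments differ as walked. It does not answer whether they differ at the same pace, and the second question is closer to what a statement about causes needs.

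The two groups may well differ in pace for reasons of setting alone. The controls are historical, and the children with Dravet syndrome are given small carrying tasks as a distraction. The protocol does not say whether the controls had such tasks.

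What is at stake is the interpretation. Identifying the causes of the gait disorder is a stated purpose of the moment analysis, and decisions on interventions are to rest on the gait results together with the follow-up.

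**Working it through.** **The plan's own figure.** "Approximately 50 participants are being sought, 30 of which are from UZA and 20 from other centres": 30 + 20 = 50, which is consistent. It is a recruitment target. The protocol gives no effect size, SD, significance level or power, so there is no calculation to reproduce.

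**Inputs to the illustration**

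- Group size n: 50 per group, if the healthy controls match the target in number. A second case uses 30 per group, because the size-matched control population is described as typical development or cerebral palsy, so the number of healthy controls is uncertain.
- r, the within-group correlation between speed and a moment: 0.3 to 0.7. Assumed.
- s, the speed deficit of the Dravet group in within-group SDs: 0.5 to 1.0. Assumed.
- Two-sided 5% test. Assumed.

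**Formula.** If the groups differ only in speed, the standardised difference in moments is d = r × s. The t-test rejects with the probability given by a noncentral t distribution with 2n − 2 degrees of freedom and noncentrality d / √(2/n). For n = 50, √(2/50) = 0.20. With r = 0.5 and s = 1.0, for example, d = 0.50, the noncentrality is 0.50 / 0.20 = 2.5, and the test rejects in 69.7% of studies.

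| r | s | d = r × s | Rejects, 50 per group | Rejects, 30 per group |
|---|---|---|---|---|
| any | 0 | 0 | 5% | 5% |
| 0.3 | 0.5 | 0.15 | 11.5% | 8.8% |
| 0.5 | 0.5 | 0.25 | 23.6% | 15.9% |
| 0.3 | 1.0 | 0.30 | 31.8% | 20.8% |
| 0.7 | 0.5 | 0.35 | 41.0% | 26.6% |
| 0.5 | 1.0 | 0.50 | 69.7% | 47.8% |
| 0.7 | 1.0 | 0.70 | 93.4% | 76.0% |

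**Check by simulation, with and without speed as covariate** (50 per group, 3000 runs per scenario, linear model with group and speed):

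| r | s | Unadjusted t-test | Speed as covariate |
|---|---|---|---|
| 0.3 | 0.5 | 11.6% | 4.1% |
| 0.5 | 1.0 | 70.3% | 4.6% |
| 0.7 | 1.0 | 93.4% | 5.1% |

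The simulated unadjusted rates agree with the formula. Under a speed-only difference, adjustment brings the rate back to about 5%.

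**The case against.** The strongest objection concerns a reading that goes further: a reader might infer that lower moments will be taken as muscle weakness. The protocol does not support that. It requires strength measurements alongside gait analysis to confirm weakness, provides them independently of gait, and says that a moment is not muscle action alone. Its wording on cause is also hedged. This objection stands, so the point is limited to mistaking pace for some biomechanical cause. The safeguards do not close that gap, because neither a strength test nor EMG shows how much of a moment difference is due to speed. They also have limits: the protocol says manual strength tests are hard for these children to follow, and EMG may not be obtained from all of them.

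Other objections stand in part:

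- The statistical section speaks of gait parameters and does not name moments, and the only reference-data comparison described under Data analysis concerns kinematics. Including moments is an inference. It is the natural one, since moments are the protocol's route to causes.
- Covariates are often left to a separate statistical analysis plan, which is not at hand. Here, however, the protocol names the test under its own statistical heading, and a t-test takes no covariate. The annual-change analysis is different: it is called only a mixed models design, with no covariates listed or excluded, so whether speed enters there is an open detail and no finding.
- If the groups walk at different speeds, their moments as walked do differ, and the t-test is right to reject for that question. This stands. The excess over 5% counts only against a claim about moments at equal pace.
- Preferential speed is deliberate, to obtain a natural pattern. This stands too; the recording condition is not at fault.

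A reader might also infer that a strength-related cause should be claimed only if the difference remains at equal speed. That does not follow. Weakness may itself slow the child. If strength acted on moments only through speed, the adjusted test would reject at about its nominal 5%, and a real effect would be missed almost always.

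**Conclusion.** The point holds in a limited form. The protocol combines self-selected speed, a tentative causal reading of joint moments and an unadjusted two-group test against existing data, with no stated provision for speed. A difference in pace could therefore appear as a difference in moments and be mistaken for a biomechanical cause.

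The size cannot be fixed from the protocol. Under the assumed inputs, a speed-only difference is significant in about 11% to 93% of studies with 50 per group and 9% to 76% with 30. If the groups walk at the same speed, the rate is 5% and the problem disappears. The conclusion rests on three assumptions: that children with Dravet syndrome walk slower, that moments correlate with speed to the assumed degree, and that moments are among the gait parameters tested. It calls for a cheap improvement to the analysis; the recording procedure need not change.

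**What to change.** Keep preferential speed, and keep the raw comparison as the description of gait as walked. Then:

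1. Report walking speed, scaled to leg length, for each group.
2. For joint moments, add a second comparison with scaled speed as covariate, or against control trials of similar speed.
3. Show both results wherever moments are discussed as causes, and interpret them together with the strength measurements and EMG. Neither result should decide the question of cause alone.

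The cost is one covariate and one further set of results. For the children with Dravet syndrome, speed can be derived from the motion data already recorded. Whether speed and leg length are available in the control database must be confirmed first. If speeds in the two groups hardly overlap, neither the covariate model nor the matching will be reliable, and this should be reported. The main downside is that slow walking may be a consequence of the disorder, so the adjusted result can understate a real effect. That is why the raw result must stay beside it.
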